3 OBJECTIVES AND ENDPOINTS

Objectives	Endpoints	Justification for Endpoints
Primary		
To evaluate the safety, usability, acceptability, and willingness of using the adapted WebApp among a randomized sample of 300 first year university students.	Safety will be assessed through qualitative interviews Usability will be measured through the System Usability Scale (Brooke, 1986)	The endpoints are common outcomes of interest for studies of technological interventions. These outcomes will be measured throughout the study, to observe changes overtime with continued exposure to

	
Acceptability will be measured through an investigator generated scale
 
Willingness to use will be assessed through qualitative interviews
	
the intervention. These endpoints are important outcomes, as interventions must be safe, acceptable, and usable to ensure broad scale uptake.
	
Secondary	
To complete preliminary evaluations on efficacy measures such as sexual victimization/perpetration, rape myth acceptance, and power in sexual relationships to allow for power calculations for a future R-level submission.
	
Sexual victimization/perpetration will be measured using the Sexual Experiences Survey (Koss et al., 2007)
 
Rape myth acceptance will be measured using the Illinois Rape Myth Acceptance – Modified (McMahon & Farmer, 2011)
 
Relationship power differentials will be measured using the Sexual Relationship Power Scale (Pulerwitz, Gortmaker, & DeJong, 2007)
	
The endpoints are important, as the WebApp under study is a primary sexual violence prevention intervention. As such, experiences of sexual violence victimization and perpetration, as well as rape myth acceptance and relationship power (both upstream factors contributing to sexual violence perpetration) are outcomes of interest. Though this pilot study is not powered to detect changes in these secondary outcomes, obtaining data for power calculations for a larger study is a key component of this study.

4 STUDY DESIGN

4.1 OVERALL DESIGN

This project builds on the current momentum to address the primary prevention of sexual violence within United States institutions of higher education as well as the proliferation of web-based applications. We will test a culturally and contextually adapted evidence-based application, MKit, with incoming university students (age range expected to be 18-25 years old) using the ADAPT-ITT (Assessment, Decision, Adaptation, Production, Topical experts, Integration, Training, Testing) framework (Wingwood & DiClemente, 2008). The web-based application was created through collaboration with students, stakeholders, and topical experts and developed by the Center for Health Communications Research (CHCR) through a modification of the pre-existing iCON platform. This process will allow us to translate clinical research on the life skills approach to impact the health and well-being of university students.

A before-and-after quasi-experimental, mixed-method pilot design will be used to gather acceptability and safety data as well efficacy trends. Two residence halls (West Quad and South

Quad) at the University of Michigan will be randomized to receive either: (1) the control arm (n=150) which will receive usual care only (all incoming students receive three programs about healthy relationships and sexual violence including Haven, Relationship Remix, and Change it Up) or (2) the usual care (n=150) described above and the web-based intervention (MKit). We will use cluster-randomization by residence hall (to minimize contamination associated with individual-level randomization of students living in the same residence hall). Following the informed consent process, students in both conditions will complete a baseline survey of 85 questions. Baseline measures will include: 1) demographic data, 2) 20 items from the Sexual Experiences Survey (SES) will measure past experiences with sexual violence (Koss et al., 2007), 3) investigator developed questions on knowledge about sexual violence, 4) 22 items from the modified Illinois Rape Myth Acceptance Scale to measure attitudes endorsing rape myths (McMahon & Farmer, 2011), and 4) 6 items from the Sexual and Relationship Power Scale (SRPS) will measure the multidimensional nature of power in relationships (Pulerwitz & Barker, 2000). All of these are measures have been validated and used extensively in the United States to measure knowledge and attitudes related to gender based violence. Following the survey, students in the Intervention group will be given the opportunity to interact with the application at their own pace, choosing which content to view in the order they prefer.

The Control group will only receive the usual care delivered to all incoming University of Michigan students, which includes Haven (an online course about sexual violence), Relationship Remix (an interactive program about healthy relationships and sexual violence delivered by peers), and Change it Up (a theater based performance on bystander intervention). The Intervention group will receive the usual care described above as well as access to the adapted web-based application. They will be encouraged to interact with the web-based application throughout the study. Data will be collected on the content viewed by the participants, as well as the amount of time they spend within each content area, and the order in which they view the content.

At 3 and 6 months, we will repeat all baseline measures in both groups. Participants in the Intervention group will also be asked to complete the 10-item System Usability Scale (Brooke, 1996) and an investigator creates 5-item acceptability scale.

Post-intervention semi-structured interviews will be conducted with 25 participants including 15 participants from the intervention group and 10 participants from the control group to assess perceived safety, reaction to content, desirability, willingness to continue using the content, and willingness to recommend the content to others. Prior to commencing the interviews, we will ask each participant to complete a paper demographic survey.

4.2 SCIENTIFIC RATIONALE FOR STUDY DESIGN

This is a before-and-after quasi-experimental, mixed-method pilot design with three survey collection points and a post-study semi-structured interview component. This study will be performed with healthy college students to determine the safety, acceptability, and usability of the WebApp.

The endpoints are common outcomes of interest for studies of technological interventions. These outcomes will be measured throughout the study, to observe changes over time with continued exposure to the intervention. These endpoints are important outcomes, as interventions must be safe, acceptable, and usable to ensure broad scale uptake. As the WebApp under study is a

primary sexual violence prevention intervention, experiences of sexual violence victimization and perpetration, as well as rape myth acceptance and relationship power (both upstream factors contributing to sexual violence perpetration) are outcomes of interest. Though this pilot study is not powered to detect changes in these secondary outcomes, obtaining data for power calculations for a larger study is a key component of this study.

This study compares usual care for the prevention of sexual violence with care as usual plus the intervention. Both groups will receive interventions currently in place, ensuring that standard care is not withheld from any participant. As the intervention under study is intended to supplement and reinforce current primary prevention programming, the study design will measure the acceptability and preliminary efficacy of broad scale-up of the intervention to the broader college campus.

4.3 JUSTIFICATION FOR DOSE

Intervention group participants will have six months to interact with the WebApp content, as this time period should present sufficient time for meaningful short-term change in the outcomes of interest. Further, the study will run for the duration of the school year, allowing study staff to follow students from the beginning of the school year to the end of the school year as they interact with the WebApp content.

4.4 END OF STUDY DEFINITION

A participant is said to have completed the study if he or she has completed all three surveys, including the baseline, 3-month, and 6-month surveys, shown in the SOA.

5 STUDY POPULATION

5.1 INCLUSION CRITERIA

For the pilot study, individuals who meet the following criteria will be considered eligible to participate in the study:

1. Currently enrolled as a student at the participating university
2. Participated in Relationship Remix in Fall 2017 as a first-year or transfer student
3. Willing to participate in the study
4. Able to speak and read English

For the semi-structured interviews, individuals who meet the following criteria will be considered eligible to participate in the study:

1. Currently enrolled as a student at the participating university
2. Participated in Relationship Remix in Fall 2017 as a first-year or transfer student
3. Participated in the pilot study
4. Willing to participate in the study
5. Able to speak and read English

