5.2 EXCLUSION CRITERIA

Not Applicable

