5.4 SCREEN FAILURES

As all participants will be recruited directly from Relationships Remix, a program for currently enrolled University of Michigan students, all participants are exceedingly likely to be eligible for the study given the inclusion criteria.

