5.5 STRATEGIES FOR RECRUITMENT AND RETENTION

Students from the target sample, first-year University of Michigan college students, will be recruited for the study. Two residence halls (West Quad and South Quad) at the University of Michigan will be randomized to receive either: (1) the control arm (n=150) which will receive usual care only (all incoming students receive three programs about healthy relationships and sexual violence including Haven, Relationship Remix, and Change it Up) or (2) the usual care (n=150) described above and the web-based intervention (MKit). We will use cluster-randomization by residence hall (to minimize contamination associated with individual-level randomization of students living in the same residence hall). At the end of the Relationship Remix program, a brief announcement will be made about the opportunity to participate in a research study about healthy relationships and palm cards will be distributed (see recruitment materials). We will recruit specifically from Relationship Remix to ensure that all experimental and control subjects receive the same primary prevention programming currently in place on campus. Interested students will receive a palm card with a link to either the MKit web-based application (Intervention) with an access code to sign-up for the website, or a link to the baseline consent and Qualtrics survey (Control) without access to the web-based application. At the end of the study, students from each condition will be invited to participate in an in-person semi-structured interview. Students will receive the invitation to participate in the semi-structured interview on the final page of their 6-month follow-up survey. Students who opt to share their email address with the study team at that time will be contacted to set-up an in-person interview based on user status for the intervention (consistent user of MKit, frequent user of MKit, minimal user of MKit) and a diverse group based on gender, race/ethnicity, and age for the control group. Semi-structured interviews will be conducted with participants from both the Control group (n=10) and the Intervention group (n=15).

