9.4.5 BASELINE DESCRIPTIVE STATISTICS

Study groups will be compared on baseline characteristics, including age, race/ethnicity, gender, student group involvement, sexual orientation, and relationship status.

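### Halls are randomised, but section 5.1 does not require living in either hall and no step matches a student's hall to the arm entered

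*Combined protocol and SAP*

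**What the plan says.** **Unit of allocation.** Sections 4.1, 5.5 and 6.3 allocate by residence hall. Section 5.5 gives the reason: "We will use cluster-randomization by residence hall (to minimize contamination associated with individual-level randomization of students living in the same residence hall". The synopsis (1.1) lists South and West Quad as the enrolling facilities, and the schedule of activities (1.3) places randomisation by hall before recruitment.

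**Eligibility.** Section 5.1 has four criteria for the pilot: current enrolment, willingness, ability in English, and "Participated in Relationship Remix in Fall 2017 as a first-year or transfer student". Section 5.2 is marked not applicable. Section 5.4 expects almost no screen failures, reasoning as follows: "As all participants will be recruited directly from Relationships Remix, a program for currently enrolled University of Michigan students".

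**Entry to an arm.** Cards are handed out after the programme. Section 5.5 describes the intervention version as follows: "palm card with a link to either the MKit web-based application (Intervention) with an access code to sign-up for the website". The control version leads instead to online consent and a survey, and gives no entry to the app. Section 10.1.1.2 adds that consent for the pilot is read and decided online by each student alone.

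**Recording and analysis.** Section 9.4.5 states: "Study groups will be compared on baseline characteristics, including age, race/ethnicity, gender, student group involvement, sexual orientation, and relationship status". Section 9.3 uses all pilot data for feasibility, usability and acceptability. Sections 9.4.1 and 9.4.3 compare the two arms by ANOVA on the secondary outcomes.

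**The concern.** Allocating by hall limits contamination only if the people in each arm live in the hall allocated to that arm. The hall restriction appears in the synopsis and the recruitment text but not in the criteria that decide who may enrol, and the programme from which students are drawn reaches well beyond two halls.

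Two things are at stake. If residents of the control hall join the intervention arm, app users live among control participants, which is the exposure that hall allocation was meant to prevent. And if students can enter an arm other than through their hall, some of the between-arm difference may reflect who chose to seek out the app. Those between-arm data are intended to inform power calculations for a later, larger study, so the problem would carry forward even though this pilot claims no power for these outcomes.

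**Working it through.** The documents give no figure for mismatched enrolment, so the main check is a reading of the text, taking three students who each hold an intervention card.

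| Student | Meets all four criteria in 5.1? | Excluded by 5.2? | Stopped by a described hall check? |
|---|---|---|---|
| Resident of the intervention hall | Yes | No | No, and should not be |
| Resident of the control hall | Yes | No | None described |
| Resident of neither hall | Yes | No | None described |

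The criteria do not separate the three rows. The same table holds for a control card, which leads straight to online consent and the survey.

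**Could a mismatch be found later?** Only if hall is recorded. Section 4.1 mentions demographic data within an 85-question baseline survey but does not itemise it. Hall is named neither in 9.4.5 nor among the subgroup variables in 9.4.7. If the survey has no hall item, sections 10.1.3 and 10.1.9.1 make it hard to add later: identifiable information is not linked to survey or app data, and emails are released in batches separate from the data.

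**Is there a rule for a mismatch?** Section 9.3 and sections 9.4.1 to 9.4.3 give none.

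**What size could it have?** Let c be the share of each arm of 150 living in the other hall. c is assumed, and nothing in the documents shows that it exceeds zero. For c = 5%, 10% and 20%, the number per arm is 150 × c = 7.5, 15 and 30. The consequence depends on how these students are analysed.

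- *By arm entered, which is how the plan reads.* The condition received agrees with the arm, so there is no mechanical dilution. If the mismatched students in one arm differ on the outcome by D from that arm's proper residents, for reasons unrelated to the app, the arm mean shifts by c × D: 0.05D, 0.10D or 0.20D. D is unknown. Any exposure of control participants to app users in their own hall comes on top.
- *By hall of residence.* With true effect δ and symmetric mixing, the observed effect is (1 − c)δ − cδ = (1 − 2c)δ. That gives 1 − 0.10 = 0.90, 1 − 0.20 = 0.80 and 1 − 0.40 = 0.60 of δ. This applies only to an analysis by hall, which the plan does not describe.

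**The case against.** The strongest reply is that the intent is plain. The two halls are the named enrolling sites, the cards differ by arm and are handed out in person after a session, the control card carries no app code, and a resident of a third hall falls outside the stated setting. If sessions were run hall by hall, few wrong cards would be issued. All of this shows that the plan does not mean to ignore hall. It does not supply a criterion or a check, and the documents do not say that sessions were hall-specific.

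Four stronger readings are tempting, and the documents do not support them.

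- A reader might infer that hall is not recorded, so that mismatches can never be found. The list in 9.4.5 is a list for comparison and is worded as not exhaustive, and the questionnaire is not reproduced. What can be said is that recording is not stated.
- A reader might infer that codes will be passed around. Section 5.5 does not say whether a code is shared or personal.
- A reader might infer that the effect shrinks by 1 − 2c. That factor does not describe a comparison of arms as entered.
- A reader might infer that arms did mix. Nothing shows this.

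It also stands that the primary objective is largely untouched. Usability and acceptability are assessed within the intervention group, and safety and willingness come from interviews. A wrong-hall student who used the app is still a real user.

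**Conclusion.** The point holds as a gap between the randomised unit and the written eligibility rules. As drafted, 5.1 admits students from the other hall or from neither, no check of hall against arm is described, and the documents do not state that hall is recorded or how a mismatch would be handled. The effect is to weaken the contamination protection and to open the secondary between-arm comparison to self-selection.

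Its size is unknown: c and D are both unstated, and c could be close to zero if recruitment was in practice separated by hall. The within-arm endpoints are little affected. Closing the gap would not remove the confounding of hall with intervention that comes from having one hall per arm; that is a separate issue. This is an inexpensive correction worth making, not a threat to the pilot's primary aim.

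**What to change.** 1. Add to 5.1: *Lives in the residence hall (West Quad or South Quad) allocated to the arm whose enrolment link is used.* Requiring residence in either hall would not be enough, because it would still admit a control-hall resident holding an intervention card.
2. Ask hall of residence at sign-up in both arms, before consent is completed, and keep the answer as a baseline variable. For a correctly placed student the arm already implies the hall, so the item adds little identifying information.
3. Make access codes single-use if they are not already. The control link carries no code, so the hall question is the main check.
4. Report how many sign-ups showed a hall and arm mismatch, and how many were turned away or enrolled in error.
5. State the analysis rule in 9.3. In the between-arm comparison, analyse any enrolled mismatch by the allocation of the student's hall as given at sign-up, and leave out residents of neither hall. The by-hall dilution shown above would then apply to any mismatches enrolled, which is a reason to stop them at entry.
6. Align the synopsis, 5.4 and 5.5 with the new criterion.

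The cost is one criterion, one survey item, possibly a code setting, and a few sentences. The downside is small: a few interested students are turned away. Hall would be self-reported, so the check is good but not complete.

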5.2 EXCLUSION CRITERIA

Not Applicable

5.3 LIFESTYLE CONSIDERATIONS

Not Applicable

5.4 SCREEN FAILURES

As all participants will be recruited directly from Relationships Remix, a program for currently enrolled University of Michigan students, all participants are exceedingly likely to be eligible for the study given the inclusion criteria.

5.5 STRATEGIES FOR RECRUITMENT AND RETENTION

Students from the target sample, first-year University of Michigan college students, will be recruited for the study. Two residence halls (West Quad and South Quad) at the University of Michigan will be randomized to receive either: (1) the control arm (n=150) which will receive usual care only (all incoming students receive three programs about healthy relationships and sexual violence including Haven, Relationship Remix, and Change it Up) or (2) the usual care (n=150) described above and the web-based intervention (MKit). We will use cluster-randomization by residence hall (to minimize contamination associated with individual-level randomization of students living in the same residence hall). At the end of the Relationship Remix program, a brief announcement will be made about the opportunity to participate in a research study about healthy relationships and palm cards will be distributed (see recruitment materials). We will recruit specifically from Relationship Remix to ensure that all experimental and control subjects receive the same primary prevention programming currently in place on campus. Interested students will receive a palm card with a link to either the MKit web-based application (Intervention) with an access code to sign-up for the website, or a link to the baseline consent and Qualtrics survey (Control) without access to the web-based application. At the end of the study, students from each condition will be invited to participate in an in-person semi-structured interview. Students will receive the invitation to participate in the semi-structured interview on the final page of their 6-month follow-up survey. Students who opt to share their email address with the study team at that time will be contacted to set-up an in-person interview based on user status for the intervention (consistent user of MKit, frequent user of MKit, minimal user of MKit) and a diverse group based on gender, race/ethnicity, and age for the control group. Semi-structured interviews will be conducted with participants from both the Control group (n=10) and the Intervention group (n=15).

The Intervention group will receive the usual care described above as well as access to the adapted web-based application. They will be encouraged to interact with the web-based application throughout the study. Built-in reminders to the web-based application, an email alert, and a text-message alert (if the participant chooses to share their phone number) remind participants about their goals and encourage retention and continued engagement.

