1 PROTOCOL SUMMARY

1.1 SYNOPSIS

Participant Duration:	For pilot study – 9 months
Title:	MKit: A Pilot Study Testing a Life Skills Application to Address Interpersonal Relationships in College
Study Description:	This study utilizes implementation science principles to culturally adapt a pre-existing web-based application (WebApp) for use with college students. We will use the ADAPT-ITT process to adapt the WebApp to a diverse (race, ethnicity, gender/sexual identity) college population with a focus on life skills and holistic self-care as reinforcement to currently available primary prevention programming available to freshman students. Our hypothesis is that the adapted WebApp will be safe, acceptable, and students will be willing to use it as a reinforcement to current university primary prevention programming.
Objectives:	
• Primary: To evaluate the safety, usability, acceptability, and willingness of using the adapted WebApp among a randomized sample of 300 first year university students.• Secondary: To complete preliminary evaluations on efficacy measures such as sexual victimization/perpetration, rape myth acceptance, and power in sexual relationships to allow for power calculations for a future R-level submission.
Endpoints:	
• Primary: Safety (qualitative interviews), Usability (System Usability Scale, Brooke, 1986), Acceptability (investigator generated), and willingness to use (qualitative interviews).• Secondary: Sexual victimization/perpetration (Sexual Experiences Survey, Koss et al., 2007), Illinois Rape Myth Acceptance – Modified (McMahon & Farmer, 2011), Sexual Relationship Power Scale (Pulerwitz, Gortmaker, & DeJong, 2007)
Study Population:	300 first year university students (150 Control Group, 150 Intervention Group)
Phase:	Pilot
Description of Sites/Facilities Enrolling Participants:	University of Michigan Residence Halls (South and West Quad)
Description of Study Intervention:	Web-based app that uses a life skills approach to address healthy relationships and sexual violence.
Study Duration:	2 years 9 months

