9.3 POPULATIONS FOR ANALYSES

All data collected through the pilot study process will be utilized for the analyses related to feasibility, usability, and acceptability. The data collected from the semi-structured interview subjects will be utilized to analyze the safety of the application and the willingness of participants to use the application.

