9.4.2 ANALYSIS OF THE PRIMARY ENDPOINT

The safety of the WebApp and the willingness of participants to use the WebApp will be assessed through post-intervention semi-structured interviews, conducted with 25 participants including 15 participants from the intervention group and 10 participants from the control group. The usability for the WebApp will be assessed at two time points (3-months and 6-months) using the 10-item System Usability Scale (Brooke, 1996). The acceptability of the WebApp will be assessed at two time points (3-months and 6-months) using an investigator created 5-item acceptability scale. Usability and acceptability scores will be assessed among those in the intervention group.

For the semi-structured interviews, all audiotapes will be transcribed verbatim. Data analyses will be conducted using an iterative process and the constant comparative method of analysis (Glaser, 1992). Member checking will contribute to credibility through validation of the research findings by participants. A codebook will be developed after repeated high-level reading of the transcripts by the study team. Data will be coded and grouped into categories to facilitate abstraction and concept analysis. An audit trail will be established to allow others to follow the decisions made by the research team (Sandelowski & Barroso, 2003). The results of the semi-structured interviews will be used to: 1) update the content of the WebApp, as needed; 2) assess the safety of the WebApp; 3) assess the usability and willingness to use the WebApp; and 4) assess the acceptability of the WebApp.

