9.4.7 SUB-GROUP ANALYSES

Primary and secondary endpoints will be analyzed based on gender, race/ethnicity, student group involvement, sexual orientation, and relationship status.

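### Section 5.5 selects the 15 app-arm interviewees by use level only, so the interview-based safety and willingness endpoints may miss some groups the app was adapted for

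*Combined protocol and SAP*

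**What the plan says.** The synopsis (1.1) says the project will "adapt the WebApp to a diverse (race, ethnicity, gender/sexual identity) college population". Section 3 makes safety, usability, acceptability and willingness to use the primary endpoints. Section 9.3 assigns two of them to the interviews: "The data collected from the semi-structured interview subjects will be utilized to analyze the safety of the application and the willingness of participants" to use it. Section 9.4.2 fixes the numbers at "15 participants from the intervention group and 10 participants from the control group".

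Section 5.5 states how interviewees are picked from students who volunteer on the last page of the 6-month survey. In the app arm they are contacted "based on user status for the intervention (consistent user of MKit, frequent user of MKit, minimal user of MKit"). In the other arm the aim is "a diverse group based on gender, race/ethnicity, and age for the control group". The same section says controls enrol "without access to the web-based application".

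Section 9.4.7 then commits to subgroup results: "Primary and secondary endpoints will be analyzed based on gender, race/ethnicity, student group involvement, sexual orientation, and relationship status".

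**The concern.** The plan does sample purposively for demographic variety, but only in the arm that has not used the product. Controls can react to the idea of an app. They cannot say whether using it felt safe or whether they would go on using it. Those who can are selected on a different attribute.

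The omission bears on the purpose of the study. The adaptation is described in terms of race, ethnicity and gender/sexual identity. Gender and race/ethnicity are criteria for controls only. Sexual identity, which reappears as sexual orientation among the subgroups in 9.4.7, is a criterion for nobody.

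At stake is a statement that the app is safe and wanted, resting on interviews that may hold few or no users from some of the groups it was adapted for. Interviews come after the 6-month survey, so a gap noticed at analysis would be hard to fill.

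**Working it through.** **1. Is there a demographic criterion for the app arm anywhere?** Sections 4.1, 8.2, 9.4.2 and 9.4.4 also describe the interviews. Each repeats the 15 and 10 split (15 + 10 = 25) and none adds a criterion. Section 4.1 has interviewees complete a paper demographic form before the interview starts; that describes those already chosen and does not choose them.

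**2. Which endpoints are exposed?**

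| Primary endpoint | Source | Who supplies it |
|---|---|---|
| Safety | Interviews (9.3, 9.4.2, 9.4.4) | 15 app users, 10 controls without the app |
| Willingness to use | Interviews (9.3, 9.4.2) | Same |
| Usability | 10-item scale at 3 and 6 months (9.4.2) | Intervention arm, planned n = 150 |
| Acceptability | 5-item scale at 3 and 6 months (9.4.2) | Intervention arm, planned n = 150 |

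Only the first two rows depend on the selection rule. Section 9.4.2 also lists usability and acceptability among the uses of the interviews. That supplement shares the limit; the survey scores do not.

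**3. Illustrative size.** Section 9.2 reports no formal sample size calculation, so there is no figure of the plan's to reproduce. The documents give no group shares, so the share p is an assumption. If the 15 are chosen without regard to the trait:

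- P(none) = (1 − p)^15
- P(at most one) = (1 − p)^15 + 15p(1 − p)^14

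| Assumed p | Expected number, 15p | P(none) | P(at most one) |
|---|---|---|---|
| 5% | 0.75 | 0.95^15 = 46% | 83% |
| 10% | 1.5 | 0.90^15 = 21% | 55% |
| 15% | 2.25 | 0.85^15 = 9% | 32% |
| 20% | 3.0 | 0.80^15 = 4% | 17% |

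Drawing 15 without replacement from 150 students, of whom 8, 15, 22 or 30 belong to the group, gives 42%, 19%, 8% and 3% for none. The picture is the same.

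**4. What purposive selection can gain.** It can only pick from those who volunteer, and the size of that pool is not stated. At p = 5%, a pool of 30 contains nobody from the group with probability 0.95^30 = 21%. If only 15 volunteer, all are interviewed and the chance stays at 46%. Fifteen places over three use levels is about 5 each if split evenly (an assumption), so not every combination can be filled.

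**5. Can the selection be carried out?** Section 10.1.3 says email addresses will not be linked to survey or application use data, and 10.1.9.1 says emails reach study staff in batches with no data attached. Volunteers are known to the team by email. As described, neither the use-level rule nor a demographic rule can be applied unless the student supplies the information when volunteering. This already affects the present rules in both arms.

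**The case against.** Use level is a sensible first criterion: how much a student used the app bears directly on reactions to it and on willingness to continue. Controls have no use level, so demographic variety is the natural criterion there. This stands, and it is why use level should be kept.

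The diversity phrase in the synopsis describes the adaptation process. The primary objective speaks of first-year students and sets no diversity requirement for interviewees. That is fair, but 9.4.7 promises the primary endpoints by several of the same traits, so the plan itself expects to say something about these groups.

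The percentages rest on assumed shares and on selection unrelated to the trait, whereas interviewees are self-selected volunteers. This also stands; self-selection or attrition could move the figures either way.

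Three stronger readings are tempting and are not supported:

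- A reader might infer that the plan rules out a diverse app-arm sample. It does not; it only fails to provide for one.
- A reader might infer that the 9.4.7 breakdowns would have nobody to describe. Usability and acceptability are surveyed across the intervention arm, where a 5% group would be about 0.05 × 150 = 7.5 students before attrition. Adverse events may also come to light in any participant (8.3.4), although the safety endpoint itself is the interviews.
- A reader might infer that age is a wasted criterion among first-year students. Section 4.1 expects ages 18 to 25 and section 5.1 admits transfer students, so age can vary.

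**Conclusion.** The point holds as a limited design weakness. The stated criterion for the 15 interviewees who used the app is use level only, and the stated demographic criteria fall on the 10 who did not. Safety and willingness, as assessed by interview, may therefore include few or no app users from some of the groups the app was adapted for. The survey-based usability and acceptability endpoints are untouched.

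This conclusion comes from comparing sections and does not depend on the arithmetic. The arithmetic shows only that the risk is not trivial for small groups: from 46% at an assumed 5% share down to 9% at 15%, if selection is unrelated to the trait. The documents do not support saying that safety will go untested in these groups, only that the plan does not guard against it. The change is worth making because it is cheap and improves a rule already written.

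**What to change.** In section 5.5, keep use level as the first criterion for the 15 intervention interviewees. Add that, within use level and where volunteers allow, they will be chosen for variety in gender, race/ethnicity and sexual identity. Age may stay as a criterion.

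Because 10.1.3 and 10.1.9.1 keep emails apart from survey and use data, collect both use level and these attributes by optional self-report on the interview opt-in page. Self-report of the demographic attributes alone would leave the use-level rule without a source.

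Report the characteristics of those interviewed, and state in 9.4.7 that breakdowns of the interview endpoints are descriptive only.

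The cost is a sentence or two in 5.5, a line in 9.4.7 and a few opt-in items, with no extra interviews. There are three downsides. Balance on use level may be slightly looser. The gain is capped by the size of the volunteer pool. Sensitive attributes would sit beside an email address in a study where section 2.3.1 already names breach of confidentiality as a risk, so the opt-in wording and secure storage must cover this.
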